Power Analysis. Previous research¹⁰⁷ suggests that an intervention that is similar to BBTF could produce an improvement in father engagement ($d = .42$).¹⁰⁸ Assuming an effect size of $d = .42$, a one-tailed alpha of .05, and a sample size of 144 participants (72 per group), we obtained a power of .80 for this design. Assuming a 20% dropout rate, the total sample needs to be 180 participants, 90 per group.

Sample Recruitment. Three recruiters, ethnically matched to the participants and with ties to the community, were trained in minority outreach by the research team to establish relationships with fathers that supported recruitment. They were also trained to give presentations about the program to community groups. It was essential that the data collectors hired were comfortable in low-income communities, highly personable, and very patient (particularly when parents failed to show up for appointments). All program advertisements included a brief description of a self-improvement program for AA fathers, featured photographs of scenes of fathers meeting together, and provided a number to call and e-mail address for further information. We continued with the highly successful active (recruiters meet directly with potential participants) and passive (potential participants are prompted to contact the staff) recruitment strategies used in our extensive prior work in low-income Chicago communities.^{95,104,105} Recruiters met with key informants already identified from churches, barbershops, community centers, schools, day care centers, local business establishments, dry cleaners, and sports venues to obtain the anticipated broad reach. Key informants were given brochures/flyers to pass on the information to potential participants. In addition, notices were placed in church bulletins and community newspapers. Active strategies included giving presentations at community churches and other community gathering places.

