Data analysis were a repeated measures analysis of variance (RM-ANOVA) to address Hypothesis 1. The basic design for these analyses was a 2x3 design with three assessment time points (the within-subjects factor) crossed with the two treatment conditions (BBTF and the comparison group [the between-subjects factor]). The null hypothesis for all these analyses was that changes for all dependent measures (psychological well-being, parenting competence, father-mother relationship quality, material support, in-kind support, and father-child interaction) would remain constant for the two groups over time. The alternative hypothesis was that they would increase over time in the BBTF group relative to the control group. This was the interaction effect in the RM-ANOVA. An initial multivariate analysis was be conducted first to see if there was any overall effect. If the null hypothesis was rejected in the multivariate analysis, we examined the univariate analyses. We tested for violations of sphericity, and if they were in evidence, then a Greenhouse-Geisser correction was used to estimate probability values.

In order to determine when these changes occurred across the three assessment time points, a follow-up analysis was conducted with time reparameterized into a set of two orthogonal Helmert contrasts. The two contrasts were of the form (1, -1/2, -1/2; 0, 1, -1), where if the first contrast was significant, this indicated that the critical differences occurred between times 1 and 2; and if the second was significant, the changes took place between times 2 and 3. This informed us as to the transition point or points where the velocity changes were greatest between the treatment and comparison groups.

Hypothesis 2: Across both conditions, father outcomes and post-intervention ratings of father-mother relationship quality will mediate paternal involvement at 12 weeks and 24 weeks.

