This analysis used a regression approach to mediation analysis, as that described in MacKinnon, 2008.¹³³ This approach looked at the extent to which changes in paternal involvement over time were explained by changes in the father outcomes and the mother-father relationship in both the treatment and control groups. This effect was estimated using a series of three regression analyses. The dependent variable (a measure of paternal involvement) at Time 2 (12 weeks) was regressed on a dummy-coded treatment variable and the same paternal involvement measure at Time 1 (baseline). Then the mediators (father outcomes and mother-father relationship) were included in the regression models, and the change in R-squared was used to determine their impact. These analyses were repeated for Times 1 and 3 (24 weeks).

Hypothesis 3a: Relative to the attention control group, BBTF children will have improved child outcomes (behavioral, emotional, and social) at 12 weeks and 24 weeks.

The analysis of Hypothesis 3a was directly parallel those described for Hypothesis 1. The only difference was in the dependent measures, which were be child outcomes instead of paternal involvement outcomes.

Hypothesis 3b: Across both conditions, father outcomes, father-mother relationship and paternal involvement will mediate child outcomes at 12 weeks and 24 weeks.

This analysis used the same regression approach to mediation analysis described in Hypothesis 2, with the only differences being that the outcome variable was the child outcomes

rather than paternal involvement; paternal involvement acted as a mediator along with father outcomes and father-mother relationship.

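### The follow-up contrasts are each tested against zero, yet are used to say in which interval the between-group change was greatest; the two intervals are never compared

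*Combined protocol and SAP*

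**What the plan says.** In the Data Analysis section, under Hypothesis 1, the group-by-time interaction is tested first in a multivariate analysis and then, if that rejects, in univariate analyses. A follow-up then recodes time into two Helmert contrasts, (1, -1/2, -1/2) and (0, 1, -1). A significant first contrast is read as a difference arising between baseline and week 12. For the other contrast the rule is "if the second was significant, the changes took place between times 2 and 3". The paragraph closes with "This informed us as to the transition point or points where the velocity changes were greatest between the treatment and comparison groups".

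The child outcomes inherit the rule: "The analysis of Hypothesis 3a was directly parallel those described for Hypothesis 1". Tests are two-tailed at .05 unless noted otherwise, and no exception is noted for these contrasts. No test of the difference between the two interval changes appears anywhere in the document.

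**The concern.** Let A be the between-group change (BBTF minus FLP) from baseline to week 12, and B the change from week 12 to week 24. The closing sentence ranks A and B, so the null hypothesis that matters to it is A = B. The tests that are run have a different null: that each contrast is zero. One significant and one non-significant result does not show that A and B differ. The overall interaction test does not help, because it asks whether there is any effect and not which interval is larger.

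At stake is how the report describes timing: whether BBTF acts mainly during the 12-week programme, or mainly in the later period that contains the week-18 booster. This concerns any of the six Hypothesis 1 outcomes, or the child outcomes, that reach the follow-up step.

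**Working it through.** **Inputs from the documents.** The Power Analysis paragraph gives d = .42 for father engagement, "a one-tailed alpha of .05", 72 per group for analysis, and "Assuming a 20% dropout rate, the total sample needs to be 180 participants, 90 per group". Assessments are at 0, 12 and 24 weeks, so the intervals are equal.

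**The plan's own figure.** The plan states "we obtained a power of .80 for this design". Check: z = .42 × √(72/2) = 2.52; 2.52 − 1.645 = .875; power = .81. Dropout: 144/.80 = 180. Both reproduce.

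**Assumptions, because the documents do not give them.** SD 1, compound symmetry with correlation ρ from .4 to .8, independent fathers, complete data, two-sided .05, and 72 or 90 per arm. The pattern of the effect over time is also assumed.

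**What each contrast estimates** (signs set so that benefit is positive):
- First Helmert: A + B/2, variance per father 1.5(1 − ρ)
- Second Helmert: B, variance 2(1 − ρ)
- Direct comparison (1, -2, 1): B − A, variance 6(1 − ρ)

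In each case SE = √(variance × 2/n). The two Helmert contrasts are independent under compound symmetry.

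**Case 1: steady effect, 0/.21/.42.** Here A = B = .21, so neither interval is greatest. The first contrast estimates .21 + .105 = .315 and the second .21. With powers p1 and p2, the chance that exactly one is significant is p1(1 − p2) + (1 − p1)p2.

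| n per arm | ρ | z1 = .315/SE1 | p1 | z2 = .21/SE2 | p2 | exactly one |
|---|---|---|---|---|---|---|
| 72 | .4 | .315/.158 = 1.99 | .51 | .21/.183 = 1.15 | .21 | .51 |
| 72 | .6 | .315/.129 = 2.44 | .68 | .21/.149 = 1.41 | .29 | .58 |
| 72 | .8 | .315/.091 = 3.45 | .93 | .21/.105 = 1.99 | .51 | .49 |
| 90 | .4 | .315/.141 = 2.23 | .61 | .21/.163 = 1.29 | .25 | .56 |
| 90 | .6 | .315/.115 = 2.73 | .78 | .21/.133 = 1.58 | .35 | .58 |
| 90 | .8 | .315/.082 = 3.86 | .97 | .21/.094 = 2.23 | .61 | .40 |

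Simulation agrees: about 40 to 59%. At 90 per arm and ρ = .6 the split is about 50% first only and 8% second only. The lean to the first interval is built in, since z1/z2 = 1.5 × √(2/1.5) = √3 = 1.73. Using the plain baseline-to-week-12 difference in place of the first contrast gives about 40 to 67% by simulation, so correcting the coding alone does not remove the problem. The direct test rejects in about 5%.

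Passing an interaction test on the same outcome first does not protect: in a separate run (72 per arm, ρ .3 to .7, compound symmetry or AR(1)), exactly one contrast was significant in 53 to 79% of trials that passed.

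**Case 2: .42 in each interval, 0/.42/.84.** Both z values double. At n = 72, ρ = .4: p1 = .98, p2 = .63, and .98 × .37 + .02 × .63 = .38. At n = 90, ρ = .8 both powers are .99 or more and the figure is about .01. Range: about 1 to 38%.

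**Case 3: all by week 12, then held, 0/.42/.42.** Naming the first interval alone is now correct, and simulation gives it in 71 to 95% of trials (90% at n = 90, ρ = .6).

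**Power of the direct test when all of .42 falls in one interval.** At n = 72, ρ = .4: SE = √(6 × .6 × 2/72) = .316, z = 1.33, power .26. At n = 90, ρ = .8: SE = √(6 × .2 × 2/90) = .163, z = 2.57, power about .72 by simulation.

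**The case against.** The best defence is that the follow-up is mostly not comparative. Its stated aim is to find when changes happened, and for the question of whether there was change in a given interval, a test against zero is the right kind of test. Only the closing sentence speaks of the greatest change, and it allows for more than one point. This stands in part: the comparative claim rests mainly on one sentence. But naming both intervals still gives no comparison of size, and the error arises when only one is named.

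Second, a reader might infer that the rule usually misleads. The documents do not support that. They give d = .42 with no time point and no split between intervals. Since the nine sessions end by week 12, an effect complete by then is at least as natural as a steady one, and there the rule is mostly right. This objection stands in full, and the size of the problem has to be stated as conditional.

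Third, this is a follow-up. No hypothesis concerns relative timing, and the sample size and the tests of Hypotheses 1 and 3a do not use it. That also stands. A reader might infer that the main group comparisons are undermined; they are not.

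**Conclusion.** The fault is real but limited. The plan draws a comparative conclusion about two intervals from separate tests against zero and never tests their difference. No figure for how often this misleads can be given without assuming the effect pattern and the visit correlation; the three cases above run from a frequent error under a slow, even build-up to a rule that usually gives the right answer when the effect is complete by week 12. Those figures further assume compound symmetry, complete data and independent fathers. The fault is distinct from the fact that the first Helmert contrast mixes both intervals (A + B/2). It affects how timing is interpreted, not whether BBTF has an effect.

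**What to change.** Replace two pieces of the follow-up paragraph: the passage that assigns location from significance, ending "if the second was significant, the changes took place between times 2 and 3", and the closing sentence, "This informed us as to the transition point or points where the velocity changes were greatest between the treatment and comparison groups". Changing only the closing sentence would leave the significance-based rule in place beside the new one. Suggested wording:

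*For each outcome, the between-group changes from times 1 to 2 and from times 2 to 3 are reported with 95% confidence intervals. One interval is said to have had the greater change only if the group-by-time contrast (1, -2, 1) is significant; otherwise relative timing is reported as undetermined.*

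Apply the same wording to Hypothesis 3a. The same rewrite can settle the coding of the first Helmert contrast, because the adjacent changes are then reported directly.

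The cost is a change of wording and one more contrast from the same model and data. The document is written in the past tense, but this needs only reanalysis. The price is the low power shown above: relative timing will often be undetermined, even in some trials where the present rule would have named the right interval. The two confidence intervals keep the information that the data do hold.

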Data Analysis Data analysis is described with respect to the three specific aims and hypotheses that were tested. Missing data was imputed using SAS Proc MI, a multiple imputation computer program based on the work of Rubin.¹³¹ All continuous data was examined for statistical normality. Histograms were obtained for these variables, and skew and kurtosis were assessed in order to assess statistical normality. Where possible, we normalized these data using Tukey's ladder of transformation¹³² before conducting statistical analysis. SPSS for Windows (Version 11) and SAS (Version 9.1) was used for data management and statistical analysis. A two-tailed 0.05 significance level was used for all statistical tests except where noted below. All analyses were performed on an intent-to-treat basis. Outcome measures that could be successfully transformed to achieve normality were in all likelihood close enough to a normal distribution that the robust nature of the F-test made it possible to obtain reasonable p values in the study.

Descriptive statistics on the sample data for all research variables were obtained. In addition, one-way ANOVAs and chi-square analysis on the demographic and baseline research measures were performed between the intervention and control groups to determine that they

were comparable. The effects of participant attrition on the research variable were also assessed using one-way ANOVAs.

Hypothesis 1: Relative to the attention control condition, BBTF program fathers will report better father outcomes (psychological well-being, parenting competence, and father-mother relationship quality) and greater paternal involvement (material support, in-kind support, father-child interaction) at 12 weeks and 24 weeks.

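### The R-squared change used to judge mediation in Hypotheses 2 and 3b cannot show whether the program moved the mediator, and no indirect effect is specified

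*Combined protocol and SAP*

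**What the plan says.** Both mediation hypotheses are in the Data Analysis section. Hypothesis 2 reads "Across both conditions, father outcomes and post-intervention ratings of father-mother relationship quality will mediate paternal involvement at 12 weeks and 24 weeks". Hypothesis 3b reads "Across both conditions, father outcomes, father-mother relationship and paternal involvement will mediate child outcomes at 12 weeks and 24 weeks".

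Under Hypothesis 2 the plan cites a textbook regression approach and adds "This effect was estimated using a series of three regression analyses". Two model forms are then described. In the first, involvement at 12 weeks "was regressed on a dummy-coded treatment variable and the same paternal involvement measure at Time 1 (baseline"). In the second, the mediators are added, and "the change in R-squared was used to determine their impact". The procedure is repeated for 24 weeks. For Hypothesis 3b, "This analysis used the same regression approach to mediation analysis described in Hypothesis 2", with child outcomes as the dependent variable and paternal involvement joining the mediators.

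The third regression is not described. The plan writes out no regression of a mediator on treatment, no product of coefficients, no change in the treatment coefficient, and no test or interval for an indirect effect.

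Separately, Hypothesis 1 compares the arms on psychological well-being, parenting competence, relationship quality and the three involvement measures by repeated-measures ANOVA: "The alternative hypothesis was that they would increase over time in the BBTF group relative to the control group". Nothing links those results to the conclusions of Hypotheses 2 and 3b.

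**The concern.** Mediation of a program effect needs two links: treatment changes the mediator (path a), and the mediator is related to the outcome given treatment (path b). The R-squared change, taken after treatment is in the model, speaks only to path b. Fathers with better well-being or a better relationship with the mother may well be more involved in either arm, program or no program. That alone would produce a sizeable R-squared change.

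Under the stated criterion, a program that changed none of the mediators would be as likely to be reported as working through them as one that shifted them by a constant amount. Mediation accounts for two of the four stated hypotheses, and claims of this kind guide which program components are kept.

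**Working it through.** **Inputs from the plan.** The Power Analysis paragraph gives 72 fathers per group (144), 180 recruited, and d = .42 for father engagement. The Data Analysis section sets the level: "A two-tailed 0.05 significance level was used for all statistical tests except where noted below". No exception is noted for Hypotheses 2 or 3b, so the R-squared change is judged here by an F test at .05. That is a reading, since the plan names no test.

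**The plan's own figure.** None is given for mediation. The group-comparison figure reproduces: .42 × √(72/2) = 2.52; 2.52 − 1.645 = 0.875; one-sided power = Φ(0.875) = .809, against .80 stated. Also 144/(1 − .20) = 180.

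**Step 1: algebra.** Let T be treatment, Y0 baseline outcome, M = aT + U the mediator, with U free of the treatment effect, and Y = c·T + .5·Y0 + bM + e. Substituting,

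Y = (c + ab)T + .5·Y0 + bU + e.

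The base model contains T, so regressing M or Y on it removes every term in a. The residual sums of squares before and after adding k mediators (RSS0, RSS1) are therefore free of a, and so is

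F = [(RSS0 − RSS1)/k] / [RSS1/(n − 3 − k)].

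The same holds if the baseline mediator is added as a covariate (with one fewer residual degree of freedom for each) or if M is a change score. The condition is that the treatment effect on M is constant across fathers.

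**Step 2: numerical check.** In 500 simulated data sets per setting, with one or three mediators and a = 0, .2, .42 and 1.0, the largest difference in F was 9.4e-14. The mean R-squared change (one mediator, residual SD .866) was .0409, .0405, .0402 and .0390. It falls slightly as a rises, because total variance grows.

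**Step 3: size.** Assumptions not in the documents: one mediator; follow-up mediator = .5·baseline + a·T + e; outcome = .5·baseline + .42·T + b·M + e; standard normal baselines; residual SD .866 to 1 in both equations. The indirect effect is a·b with a Monte Carlo 95% interval, baseline mediator adjusted. There were two runs of 5,000 trials per setting at 72 per arm, and 3,000 trials at 90 per arm. Share of trials 'positive' when a = 0 and b = .2:

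| Criterion | 72 per arm | 90 per arm |
|---|---|---|
| R-squared change, raw mediator | 74%-77% | 83%-85% |
| R-squared change, baseline mediator adjusted | 64% | 74% |
| R-squared change, change score | 25%-35% | 32%-41% |
| 95% interval for a·b excludes zero | about 3% | about 4% |
| R-squared change and treatment-to-mediator test both p < .05 | 3%-4% | 4%-5% |

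At 72 per arm the R-squared-change rates are the same at a = .42. With b = .3 and a = 0 they are 97%-98%, 93% and 48%-62%, against about 5% for the a·b interval.

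**Step 4: cross-check.** A simpler simulation (no baseline mediator, no direct effect, 144 fathers, 4,000 trials, b = .2) gave 76.5% at a = 0 and 77.7% at a = .42 for the R-squared change. These were separate draws, so the gap is simulation noise. A joint test of both paths gave 3.9% and 54.1%: it separates the two cases and the R-squared change does not.

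**The case against.** The strongest reply is that the plan already contains both halves. Hypothesis 1 tests treatment on every variable later used as a mediator, and the R-squared change supplies the other link. Requiring both would bring the rate at a = 0, b = .2 down to 3%-4%. That is a fair account of what a linking rule could achieve, although the simulated treatment-to-mediator test is not the plan's repeated-measures ANOVA with its multivariate gate. But no such rule is written, so mediation could be reported after a null Hypothesis 1.

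Second, the undescribed third regression or the cited textbook may supply the mediator-on-treatment model. That cannot be excluded. Even so, the only criterion stated is the R-squared change.

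Third, the plan describes its aim as explaining change in involvement by change in the mediators in both arms, and both hypotheses span the two conditions. If a pooled association was the target, the R-squared change fits it, and the rates above are power to detect a real association, not error rates. This stands, but it leaves the word 'mediate' unsupported.

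Fourth, change wording favours the change-score or baseline-adjusted rows over the raw one, and the plan states no explicit pass/fail rule. Both points are fair; they affect the size, not the invariance. The constant-effect condition also matters a little: in another run, letting the effect vary between fathers (assumed SD .42 around .42) moved the rates to 81%, 70% and 33%, from about 77%, 65% and 28% with a constant effect.

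**Conclusion.** The concern holds: the mediation criterion is wrong as written. For a constant treatment effect on the mediator, the F test of the R-squared change carries no information about that effect. This is exact, whatever the slopes, residual SD or number of mediators. The percentages are illustrations that rest on the assumed slope, a single mediator and an F test at .05. What is established is that the written criterion does not support a mediation claim, not that the program failed to change the mediators or that no further model was run. It should be fixed, but it leaves the randomised comparisons in Hypotheses 1 and 3a untouched.

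**What to change.** Choose one target and state it.

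1. **If mediation is claimed.** For each mediator, specify the regression of mediator on treatment and baseline mediator (giving a), and of outcome on mediator, treatment, baseline outcome and baseline mediator (giving b). Pool over the Proc MI imputations and report a·b with a 95% interval. Claim mediation only if the interval excludes zero, and report the R-squared change as association only.
2. **If only a pooled association was meant.** Keep the R-squared change and replace 'mediate' with 'be associated with' in Hypotheses 2 and 3b.

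Under option 1, also say at which visit the mediator is measured, whether mediators enter singly or jointly, and how multiplicity is handled. If child outcomes are counted as the three named domains, there are 3 × 3 × 2 = 18 combinations for Hypothesis 2 and 6 × 3 × 2 = 36 for Hypothesis 3b, 54 in all. If every a were zero, 2.7%-4.8% of 54 is about 1.5 to 2.6 false claims. Because the document is written in the past tense, date the choice and label it post hoc if results were known.

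**Cost.** Option 2 is wording only. Option 1 is wording plus a short script on variables already collected, with fewer positive claims and lower power. With 144 fathers, one mediator and an assumed a = .42 (the plan gives that value for engagement, not for the mediators), power is about 65%-77% at b = .3 and 41%-51% at b = .2 as residual SD goes from 1 to .866. At a = .2 it is about 19%-25% and 12%-16%. Mediator-outcome confounding remains under option 1, because mediators are not randomised.

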Inclusion Criteria. Inclusion criteria were: (1) AA biological father of a child 2 to 6 years old; (2) child lived with father no more than 48 hours per week (e.g., spends the weekends with his or her father); and (3) the child lived with the biological mother (or other custodial relative such as grandmother) in the metropolitan Chicago area. These fathers are referred to as AA non-resident fathers. Additional criteria included: (1) child's mother willing to consent to complete the child assessments--[this criterion was amended in order to allow fathers access to program content even when mothers were unwilling to complete research measures]; (2) child's mother amenable to facilitating opportunities for fathers to interact with their children in order to practice skills learned in the program; and (3) father able and willing to travel to one of two intervention sites to attend a weekly program. The study was limited to fathers with a target child aged 2-6 years. The rationale for this limit was based on the developmental phase when families are most vulnerable to decreased father involvement and children are highly dependent on parenting for their growth and development.

Exclusion criteria included: (1) fathers with histories of child abuse, neglect, or violence perpetuated against the child or the child's mother (based on mother or father report).

The city of Chicago is composed of 77 community areas identified by numbers. We recruited fathers from the approximately 171,000 AA men between the ages of 18 and 65 residing in 13 predominantly AA (73-98%) community areas. These mostly low-income community areas (median income \$13,596-\$43,728), with 23% to 55% of incomes below poverty level. Based on data that reveals that more than two-thirds of AA children live in homes without their biological fathers,^{1,2} we are confident that the communities will serve as rich recruitment sites for AA non-resident fathers. We identified two conveniently located sites to conduct the programs, one located on Chicago's West Side and the other located on Chicago's South Side.

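### The target child's age (2 to 6 years) is in none of the mediation regressions, so it is a plausible confounder of the Hypothesis 3b mediator step; Hypothesis 2 has the same gap.

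*Combined protocol and SAP*

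**What the plan says.** - **Eligibility (Subjects and Setting, Inclusion Criteria).** The target child must be 2 to 6 years old. The stated reason is that this is the "developmental phase when families are most vulnerable to decreased father involvement and children are highly dependent on parenting for their growth and development".
- **Hypothesis 3a (Data Analysis).** "The analysis of Hypothesis 3a was directly parallel those described for Hypothesis 1". That model is a two-condition by three-time repeated measures ANOVA without covariates, and the effect tested is the condition-by-time interaction.
- **Hypothesis 2.** Paternal involvement at 12 weeks, and then at 24 weeks, is regressed on a treatment indicator and its own baseline value. The mediators are then added, and the gain in R-squared is the criterion.
- **Hypothesis 3b.** The same regressions are used, "the only differences being that the outcome variable was the child outcomes", and paternal involvement joins the mediators.
- **Elsewhere.** Demographic variables are compared between arms, but no rule carries any of them into a model. Randomisation is in blocks of four, with no stratification by child age described.

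**The concern.** Randomisation protects the comparison of the two programmes. It does not protect the relation between a mediator and an outcome. Fathers are not allocated to levels of involvement, well-being or relationship quality, and Hypotheses 2 and 3b look at these relations across both conditions. Anything that influences both a mediator and the later outcome can therefore produce a gain in R-squared when the mediator has no effect.

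Child age is an obvious candidate when behavioural, emotional and social outcomes are measured on children between 2 and 6. The baseline outcome in the model absorbs part of any age effect. It does not absorb all of it, because one baseline score is an imperfect measure of the child's level, and because children of different ages may change at different rates over 12 or 24 weeks. What is at stake is a claim that father involvement drives child outcomes when part of the association is due to age.

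**Working it through.** **1. Sample size used for the check.** The Power Analysis section gives d = .42, "a one-tailed alpha of .05" and 72 per group, and says "we obtained a power of .80 for this design". Check: d × √(n/2) = .42 × √36 = 2.52, and Φ(2.52 − 1.645) = .81. The required number is 2 × ((1.645 + 0.842)/.42)² = 70.1, so 71 per arm. Dropout: 144/0.8 = 180. The stated figures reproduce. They concern father engagement and are not in dispute here; they supply n = 144. For the test level, Data Analysis says "A two-tailed 0.05 significance level was used for all statistical tests except where noted below", and no exception is noted for Hypothesis 3b, so the checks below are two-sided at 5%.

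**2. Hypothesis 3b, one mediator entered as a post-intervention value, no true effect.** Assumption: age correlates r with the mediator and r with the outcome after adjustment for its baseline. The spurious correlation between mediator and outcome is then r × r = r². The t statistic is centred at about √144 × r²/√(1 − r⁴), against a critical value of 1.977.

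| r | r² | centre of t | false positives |
|---|---|---|---|
| .2 | .04 | 0.48 | about 7–8% |
| .3 | .09 | 1.08 | about 18–19% |
| .4 | .16 | 1.95 | about 48–49% |

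Simulation gave 7%, 18% and 48%, and about 5% throughout once age was in the model. With 180 fathers the simulated rates were 8%, 22.5% and 57%.

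**3. The plan's own criterion: mediators added as a block.** Assume six mediators, following the constructs listed under Hypothesis 1, with one related to age. If they are mutually uncorrelated, the block's spurious R² is r⁴ and the noncentrality is 144 × r⁴/(1 − r⁴) = 0.23, 1.18 and 3.78 at r = .2, .3 and .4. The 6-df F test then rejects in 5.9%, 10% and 25% of trials. With mediators intercorrelated .3, simulation gave 6%, 12% and 29%. With three of the six related to age it gave 7%, 18% and 52%. With age in the model, all of these simulated rates were about 5–6%.

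Across steps 2 and 3, r of .2 to .3 gives about 6% to 20% at n = 144.

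**4. How large can r be after baseline adjustment?** Suppose age explains a share R of score variance at each visit and two scores correlate ρ. Residual variance is 1 − ρ² without age and (1 − R) − (ρ − R)²/(1 − R) with it. For R = .2 and ρ = .7: 1 − .49 = .51, and .80 − .25/.80 = .4875. Age explains 1 − .4875/.51 = .044 of the residual, so r = √.044 = .21. For R = .1 and ρ = .7 the share is .02, so r = .14. For R = .3 and ρ = .5 it is .143, so r = .38. Values near .4 therefore need strong age effects and low stability, or an added effect of age on change.

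**5. How the mediator enters.** A second simulation at n = 144 let age explain 10–30% of outcome variance, with or without a 0.1 SD age effect on change. False-positive rates were:

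| Mediator entered as | age–mediator r = .2 | age–mediator r = .4 |
|---|---|---|
| post-intervention value | 6–14% | 11–40% |
| post value plus its baseline | about 5–8% | 7–15% |
| change score, stable age relation | about 5% | about 5–6% |
| post value plus age | about 5% | about 4–5% |

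**6. Hypothesis 3a.** A stable age effect cancels in change from baseline (standard error ratio 1.00). If age shifts 24-week change by s SD per SD of age, and the two scores correlate .6 (assumed), the remaining variance of change is 2 × (1 − .6) = .8. The ratio is √(.8/(.8 + s²)) = .99, .98 and .95 for s = .1, .2 and .3.

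**The case against.** - **The plan shows no age gradient.** A reader might infer from the eligibility rationale that the plan itself links age to both involvement and child outcomes among these children. It does not. The rationale describes the 2 to 6 window as a whole and says nothing about differences within it. This stands: age is a plausible confounder, not a demonstrated one, and every size above is assumed.
- **The mediators may be changes.** The Hypothesis 2 text speaks of changes in father outcomes and in the relationship, and change scores keep the error near 5% when their relation to age is stable. This stands in part. The regression step does not say in which form the mediators enter, and Hypothesis 2 itself is worded in terms of relationship ratings taken after the intervention.
- **The child scores may be age-normed.** The available text does not describe the instruments. If scores are normed, the problem shrinks, and adding age does no harm.
- **Age is only one possible confounder.** This is true. Including it does not make the mediation analysis unconfounded; it removes one obvious and already measured source.
- **Hypothesis 3a is randomised.** A reader might infer that leaving age out distorts the programme comparison or costs it much precision. Neither follows, because randomisation prevents bias and the condition-by-time test removes stable age differences.

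**Conclusion.** The concern holds for the mediation regressions, as a minor point. Child age is in none of them, the mediators are not randomised, and baseline adjustment is only a partial remedy. With assumed age correlations of .2 to .3 with both the mediator and the baseline-adjusted outcome, the mediator step at n = 144 gives roughly 6% to 20% false positives instead of 5%. The rate is higher only at larger correlations. It is near 5% with change-score mediators whose relation to age is stable, and closer to 5% if scores are age-normed.

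A reader might infer a false-positive rate near one half. That needs a correlation of about .4 on both sides, post-value entry, and either a single mediator or several that are related to age. Nothing in the documents supports that as the expected case.

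For Hypothesis 3a there is no bias. The possible gain in precision is small: a standard error at most about 5% lower for an age effect on change of up to 0.3 SD.

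**What to change.** Enter the target child's age at baseline, as a continuous variable, in every Hypothesis 3b regression before the mediators are added, and do the same in Hypothesis 2. State in the same place whether mediators enter as post-intervention values, post values with their baseline, or changes. If the analyses are complete, report the age-adjusted regressions as a sensitivity analysis. An age-by-time term in the Hypothesis 3a model is optional.

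The cost is a sentence or two in the plan and one or two degrees of freedom. No new data are needed, because the child's age has to be known to establish eligibility.
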